12.2 Subjective data

Observations of bone quality (D1-D-4) recorded by surgeons at implant placement.

Clinical observations of post-extraction soft-tissue healing

Clinical observations of soft-tissue and osseous response to dental implants

Clinical observations of overall aesthetic appearance

12.3 Outcome Endpoints

The primary efficacy parameter for implant success will be the duration of implant survival from surgical placement to 24 months post-placement across all groups. Measurement of bone height along the implant mesial and distal surfaces at 12 and 24 month follow-up evaluations will be captured from radiographic images and compared to same measurements at insertion. These measurements will be used to derive changes from baseline values.

Efficacy endpoints will include implant and prosthesis function as assessed by gingival health, bone levels and participant subjective satisfaction with the study therapy. Differences between groups will be calculated and used to determine if osseous changes and implant function are different across extraction groups and between implant groups.

Safety will be evaluated by clinical signs and symptoms of dental and medical events.

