2.3 Hypotheses and Specific Aims

Hypothesis I

Bone grafted sites preserve alveolar ridge dimensions of extraction sockets more effectively than extraction sites that have healed without grafting.

Specific Aims

- 1: Compare alveolar ridge dimensions in grafted extraction sockets to that of sites healed without grafts after 8 weeks of post-extraction healing.

Hypothesis II

The addition of growth factors to bone grafting materials will enhance osseous and soft-tissue healing.

Specific Aims

- 2: Assess the efficacy of bone grafting with and without enrichment with growth factors to preserve the volume of bone in extraction sockets.

- 3: Compare soft tissue healing between groups at week-1, week-2, week-4 and after 8 weeks of post-extraction healing

- 4: Assess quantitative bone fill across groups after 2 months of post-extraction healing
- 5: Compare qualitative bone fill across groups after 2 months of post-extraction healing.
- 6: Assess and compare the relationship of osseous healing and implant stability at insertion across groups after 2 months of post-extraction healing.

Hypothesis III

Laser Thread Textured (LTT) dental implant will help preserve longitudinal peri-implant crestal bone more effectively than implants with Resorbable Blast Texturing (RBT).

Specific Aims

- 7: Assess the efficacy of LTT and RBT surface topographies when surgically implanted into extraction sockets.
- 8: Assess peri-implant soft-tissue healing adjacent to LTT and RBT surfaced implants.
- 9: Assess changes in longitudinal crestal bone level across extraction groups and between implant groups at 12 and 24 months after surgical implant placement.

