This SA will be addressed using mixed-model ANOVA to compare mean bone volume among the four groups. Post-hoc pairwise comparisons will use Tukey's test. The effect of growth factors enrichment will be addressed using contrasts and F-tests to compare the mean of Group-4 with those of each of the other groups. If there is not a significant difference among the group means of Groups 1-3, the combined mean of these three groups will be compared with that of Group-4.

SA-3: Compare soft tissue healing between groups at week-1, week-2, week-4 and after 8 weeks of healing.

The analysis of SA-3 will be mixed-model ANOVA including measurements of healing made at each time points. Time will be included in the model in order to account for unequal spacing of the observational times. The statistical test that will be of primary interest will be the F-test for Group by time interaction.

SA-4: Assess quantitative bone fill across groups after 8 weeks post-extraction healing.

Qualitative bone fill will be compared among four groups using mixed-model ANOVA and the 8 week measurement only. Post-hoc pairwise comparisons will use Tukey's test.

SA-5: Compare qualitative bone fill across groups after 8 weeks post-extraction healing.

Percent new bone, percent residual graft, and percent soft-tissue will be compared among the four groups using ANOVA. For this analysis, there will be a single measurement of each of the variables per participant, so correlated observations will not be an issue in the analysis. Post-hoc pairwise comparisons will use Tukey's test.

SA-6: Assess the relationship of osseous healing and implant stability at insertion across groups after 8 weeks post-extraction healing.

This SA will be addressed by including the implant stability measure as a predictor variable in the analysis of osseous healing. The statistical test that will be of primary interest for this analysis will be the two-factor interaction of stability and group.

Hypothesis III

Laser thread-textured (LTT) dental implant will preserve longitudinal peri-implant crestal bone more effectively than implants with Resorbable blast texturing (RBT).

SA-7: Assess the efficacy of LTT and RBT surface topographies when surgically implanted into extraction sockets.

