This SA will be addressed using a survival analysis approach. The primary outcome measure will be presence of signs and symptoms of infection at the implant site, since implant failure is expected to be rare to non-existent. Frequencies of occurrence of infection will be tabulated for each implant type.

Cox proportional hazards regression will be used to evaluate the rates of infection for LTT and RBT implants, allowing for adjustment for potential confounding variables and covariates. A blocking variable representing the individual subject will be included in order to reflect multiple implants per study subject.

SA-8: Assess peri-implant soft tissue healing adjacent to LTT and RBT surfaced implants

The JEMPT index will be evaluated at the time of final restoration and at 12 and 24 months follow-up evaluations. Mixed model ANOVA will be used to compare changes over time between implant types. The statistical test that will be of primary interest is the implant type by time interaction.

SA-9: Assess changes in the longitudinal crestal bone levels across extraction groups and between implant groups at 12 and 24 months after surgical placement.

The analysis for the SA will be mixed-model ANOVA, accounting for multiple observations per subject. The statistical test that will be of primary interest is the F-test for surface type by time interaction.

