Power estimation for the comparison of bone height measurements (SA-7), for comparison of changes in JEMT index (SA-8) and of changes in crestal bone levels (SA-9) between the two implant types was based on a t-test. The proposed sample size would provide 70% power to detect a medium effect size, and 80% power to detect a difference of 0.565sd between the groups. For SA-8 and SA-9, sd refers to the within-group standard deviation of changes across time.

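### Sections 12.3 and 12.4 give the implant stage two different primary outcomes, survival and infection, and neither measures the crestal bone that Hypothesis III is about

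*Combined protocol and SAP*

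**What the plan says.** Four parts of the combined protocol and SAP bear on this.

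- **Section 12.3, Outcome Endpoints:** the section states "The primary efficacy parameter for implant success will be the duration of implant survival from surgical placement to 24 months", and applies this to every group. The same paragraph defines bone-height change from insertion to 12 and 24 months. The next lists bone levels among several efficacy endpoints. Only survival is called primary.
- **Section 12.4, SA-7:** a survival-analysis approach in which "The primary outcome measure will be presence of signs and symptoms of infection at the implant site", the reason given being "since implant failure is expected to be rare to non-existent", said of implant failure. Infection is then compared between collars by Cox regression.
- **Section 12.4, Hypothesis III and SA-9:** the hypothesis is that LTT preserves peri-implant crestal bone better than RBT. SA-9 analyses crestal bone level by mixed-model ANOVA: "The statistical test that will be of primary interest is the F-test for surface type by time interaction".
- **Section 12.5:** power is given for infection (SA-7), for bone height (labelled SA-7), for the soft-tissue index (SA-8) and for crestal bone change (SA-9). None is given for survival.

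**The concern.** A reader who wants to know which result decides the implant stage gets survival from Section 12.3 and infection from SA-7. Neither records what the collar does to crestal bone. By the plan's own expectation survival will yield few or no failures, so the outcome that Section 12.3 calls primary is likely to look the same in both collar groups whatever happens to the bone.

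Two things are at stake. An uninformative survival result could stand as the declared primary efficacy finding. And because the two sections disagree, the choice of lead outcome stays open until someone settles it, possibly after the data are seen. The bone-height power figure filed under SA-7 adds to the confusion, since the SA-7 analysis contains no bone-height comparison.

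**Working it through.** **Inputs from the documents.** Effective sample size 50 per collar group (Section 12.5, SA-7 power); two-sided 5% level (Section 12.5); 80 participants (Sections 3.1 and 12.5), all of one participant's sites receiving the same collar (Section 4.4).

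**Inputs assumed.** The plan gives no implant failure rate, so the rates below are assumptions shown as a range. Equal allocation to the two collars is also assumed; the ratio is not stated but is implied by 50 per group.

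**1. The plan's figure for crestal bone (SA-9).** Two-sample t-test, n = 50 per group, 98 degrees of freedom, noncentrality d × √(n/2) = d × 5.
- d = 0.50: noncentrality 2.50, power 69.7% (plan: 70%).
- d = 0.565: noncentrality 2.825, power 79.9% (plan: 80%).

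The plan's figures are reproduced.

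**2. How many failures survival would need.** Section 12.4 sets out no between-group test of survival, so Fisher's exact test on failures by 24 months serves as a yardstick. If all k failures fall in one collar group, the two-sided p-value is 2 × C(50,k) / C(100,k).
- k = 5: 2 × 2,118,760 / 75,287,520 = 0.056.
- k = 6: 2 × 15,890,700 / 1,192,052,400 = 0.027.

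Fewer than six failures in total can never reach p<0.05, and exactly six do so only if all are in one group.

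**3. Power at assumed failure rates.** Exact Fisher power, 50 v 50, summing the binomial probabilities of all outcomes with p ≤ 0.05:

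| Assumed failure rates | Power |
|---|---|
| 2% v 4% | 0.6% |
| 2% v 6% | 3.2% |
| 0% v 5% | 3.8% |
| 5% v 10% | 6.3% |

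At 1% failure in both groups, the chance of no failure among 100 effective implants is 0.99^100 = 37%. With no failures, no hazard ratio can be estimated.

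**4. Does using duration help?** Events needed for 80% power at a hazard ratio of 3.2 (the same size as the odds ratio that the plan uses for infection), with (1.960 + 0.842)² = 7.85:
- Schoenfeld: 4 × 7.85 / (ln 3.2)² = 23.2, so 24 failures.
- Freedman: 7.85 × (4.2/2.2)² = 28.6, so 29 failures.

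Among 100 effective implants that means 24% to 29% failing, which does not fit an event expected to be rare to non-existent.

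**The case against.** The strongest reply is that Hypothesis III is already properly tested. Section 12.3 defines bone-height change and says that group differences will show whether osseous changes differ between implant groups. SA-9 names its own test of primary interest, and Section 12.5 powers it. The plan is organised by specific aim, and the words in Section 12.3 are qualified: survival is primary for implant success, a construct with its own criteria in Sections 10.2 and 10.3. SA-7 also recognises that failures will be rare and for that reason turns to infection.

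Most of this stands, and it limits the point. A reader might infer from Section 12.3 that the trial cannot answer Hypothesis III, or that crestal bone has been demoted to a secondary endpoint. The documents support neither: SA-9 tests it, and no endpoint is labelled secondary. A reader might also infer a planned survival comparison that is bound to be null. Section 12.4 specifies no such comparison, so the Fisher figures show how little survival could tell; they do not describe a planned test. Nor are there three rival lead outcomes, because Section 12.5 attaches a power figure to bone height under SA-7 without calling it primary.

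What the reply does not remove is the conflict. Section 12.3 was not aligned with SA-7, and infection measures crestal bone no better than survival does. If Section 12.3 meant only to define implant success, then it names no primary efficacy endpoint for Hypothesis III, and the same wording change is needed.

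**Conclusion.** The point holds as an inconsistency in endpoint designation. Sections 12.3 and 12.4 name different primary outcomes for the implant stage, and the outcome that tests Hypothesis III has no primary status in Section 12.3, although it is measured, modelled and powered.

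The size depends on the failure rate, which the plan does not give. Across the assumed pairs above, from 2% v 4% to 5% v 10%, power on survival is 0.6% to 6.3% at 50 effective implants per collar, against about 70% for crestal bone at 0.50 sd. The need for at least six failures rests only on the 50 per group, the 5% level and the choice of Fisher's test.

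One might go further and ask for a bone-level criterion in the success definition of Section 10.3. That section defines clinical success and already covers peri-implant radiolucency, so no change there is needed.

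**What to change.** 1. **Section 12.3:** name change in crestal bone height from insertion through 12 and 24 months, LTT v RBT, as the primary efficacy endpoint for Hypothesis III, tested by the surface type by time interaction of SA-9. State that insertion is one of the time points in the model. If only the 12- and 24-month changes were entered, the interaction would ask only whether the collar difference shifts between those two visits.
2. **Sections 12.3 and 12.4 (SA-7):** report implant survival and site infection by collar as supporting or safety outcomes, with counts and exact confidence intervals that allow for several implants per participant. One way is to count participants with at least one event, since each participant has only one collar type. Reword SA-7's claim to a primary outcome measure to match.
3. **Section 12.5:** delete the reference to bone height under SA-7. The same sentence already covers SA-9.

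The cost is wording. The radiographs at insertion, 12 and 24 months are already scheduled (Section 8.2), and the change from baseline is already defined. There are two downsides. Survival loses its primary label. The new primary has stated power of 70%, not 80%, at a medium effect, and that figure is for a t-test on changes. If participants averaged one site each (40 per collar, no losses), the same t-test gives about 60%. Section 12.5 should say so openly.

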12.4 Statistical Analysis

The general approach to statistical analysis of the study aims will be based on mixed-model analysis of variance (ANOVA). This approach will accommodate the inclusion of correlated observations due to study subjects potentially contributing measurements of more than one single tooth site to the analysis.

The sample distributions will be examined for each outcome variable. If these distributions depart substantially from normality, transformations of the data will be evaluated. If normality cannot be established by transformation, rank-based analyses will be used.

Subjects will be included as a random effect on the analyses that include multiple observations per subject. For analysis of histological data, only one tooth site per subject will be evaluated and the model will not include a random effect.

Smoking status will be included in all models in order to account for differences in response between smokers and non-smokers, and so that the analysis will correspond to the study's randomization strategy. Comparisons between smokers and non-smokers are not a primary interest in the study.

For aims in which interaction terms are of interest, significant interaction terms will be investigated using plots of least square means and separate post-hoc analyses for individual time points.

Hypothesis 1

Differences among the four groups will be evaluated by the overall F-test for the ANOVA. Pairwise comparisons among group means will be conducted using Tukey's test. Contrasts will be constructed to address each specific aim (SA).

SA-1: Compare alveolar ridge dimensions in grafted extraction sockets to that of sites healed without grafts after 8 weeks of post-extraction healing.

This SA will be addressed by comparing the combined mean of the three graft groups (FDBA/TCP, DDBA/TCP/PRP, FDBA/TCP/PDGF) with that of the CONTROL group by calculating a contrast and the corresponding F-test. Pairwise comparisons among means will be conducted using Tukey's test..

Hypothesis II

The addition of growth factors to bone grafting materials will enhance osseous and soft tissue healing.

SA-2: Assess the efficacy of bone grafting with and without enrichment with growth factors to preserve the volume of bone in extraction sockets.

This SA will be addressed using mixed-model ANOVA to compare mean bone volume among the four groups. Post-hoc pairwise comparisons will use Tukey's test. The effect of growth factors enrichment will be addressed using contrasts and F-tests to compare the mean of Group-4 with those of each of the other groups. If there is not a significant difference among the group means of Groups 1-3, the combined mean of these three groups will be compared with that of Group-4.

SA-3: Compare soft tissue healing between groups at week-1, week-2, week-4 and after 8 weeks of healing.

The analysis of SA-3 will be mixed-model ANOVA including measurements of healing made at each time points. Time will be included in the model in order to account for unequal spacing of the observational times. The statistical test that will be of primary interest will be the F-test for Group by time interaction.

SA-4: Assess quantitative bone fill across groups after 8 weeks post-extraction healing.

Qualitative bone fill will be compared among four groups using mixed-model ANOVA and the 8 week measurement only. Post-hoc pairwise comparisons will use Tukey's test.

SA-5: Compare qualitative bone fill across groups after 8 weeks post-extraction healing.

Percent new bone, percent residual graft, and percent soft-tissue will be compared among the four groups using ANOVA. For this analysis, there will be a single measurement of each of the variables per participant, so correlated observations will not be an issue in the analysis. Post-hoc pairwise comparisons will use Tukey's test.

SA-6: Assess the relationship of osseous healing and implant stability at insertion across groups after 8 weeks post-extraction healing.

This SA will be addressed by including the implant stability measure as a predictor variable in the analysis of osseous healing. The statistical test that will be of primary interest for this analysis will be the two-factor interaction of stability and group.

Hypothesis III

Laser thread-textured (LTT) dental implant will preserve longitudinal peri-implant crestal bone more effectively than implants with Resorbable blast texturing (RBT).

SA-7: Assess the efficacy of LTT and RBT surface topographies when surgically implanted into extraction sockets.

This SA will be addressed using a survival analysis approach. The primary outcome measure will be presence of signs and symptoms of infection at the implant site, since implant failure is expected to be rare to non-existent. Frequencies of occurrence of infection will be tabulated for each implant type.

Cox proportional hazards regression will be used to evaluate the rates of infection for LTT and RBT implants, allowing for adjustment for potential confounding variables and covariates. A blocking variable representing the individual subject will be included in order to reflect multiple implants per study subject.

SA-8: Assess peri-implant soft tissue healing adjacent to LTT and RBT surfaced implants

The JEMPT index will be evaluated at the time of final restoration and at 12 and 24 months follow-up evaluations. Mixed model ANOVA will be used to compare changes over time between implant types. The statistical test that will be of primary interest is the implant type by time interaction.

SA-9: Assess changes in the longitudinal crestal bone levels across extraction groups and between implant groups at 12 and 24 months after surgical placement.

The analysis for the SA will be mixed-model ANOVA, accounting for multiple observations per subject. The statistical test that will be of primary interest is the F-test for surface type by time interaction.

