3.0 STUDY POPULATION

3.1 Entrance Criteria

Eighty healthy adult patients (20 in each group) of any ethnicity or gender whose treatment plan includes extraction of maxillary anterior teeth and/or mandibular and/or maxillary pre-molars and their replacement with root-form dental implants will be consecutively recruited for enrollment in the study.

The study will include an initial minimum of six time-sensitive, clinic visits over eight consecutive weeks. Implants will be placed 8 weeks after extractions. Following implant placement, additional visits, necessary for health maintenance and implant restoration, will be scheduled at the study dentist's discretion. Participants will return for two follow-up visits at 12 and 24 months after implant placement.

Only treatment of non-adjacent sites will be included in the database. Each participant may have up to four non-adjacent sites selected for inclusion as study treatment sites.

Participants must be at least 19 years old with demonstrated ability to understand the proposed treatment recommendations and prognosis and be able to provide informed consent, in English, without the aid of ad-hoc translation from another language. Decisionally-impaired adults and/or minors, who cannot consent for themselves, will not be enrolled; women who are pregnant or lactating at the time of enrollment will be excluded. Women will be tested for current pregnancy status.

Prior to enrollment, prospective participants must agree to be available for the entire duration of the study, be compliant with needed study-related evaluations and demonstrate a willingness to comply with strict time-line requirements. Certain health and medication exclusions apply (table 1).

Table 1 Entrance Criteria

Inclusion	Exclusion
Existence of one or more non-adjacent teeth in the aesthetic zone that are scheduled for extraction	Pregnancy or nursing at the time of enrollment
Healthy enough to undergo the proposed therapy without compromise to their existing health status	Previous malignant neoplasm
Demonstrated willingness to comply fully with protocol time-line and procedural requirements	A known hypersensitivity to β -TCP or rhPDGF-BB
At least nineteen years old	A known hypersensitivity to Titanium metal
Able to read and understand written English without the aid of ad hoc interpretation	Any health condition that in the opinion of the clinical investigators may adversely affect bone healing

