4.4 Randomized Implant Groups

Each subject will receive two-stage dental implants with the same overall design features with two different surface treatments at the implant collar. Subjects with multiple sites will receive the same implant design in all study sites.

Group-A: Laser Thread Texturing (LTT) collar surface topography

Group-B: Resorbable Blast Texturing (RBT) collar surface topography

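### The subject-only random effect named in section 12.4 does not cover visits within sites within subjects, so the time-interaction tests of SA-3, SA-8 and possibly SA-9 can have wrong error bars when participants have several sites

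*Combined protocol and SAP*

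**What the plan says.** Section 12.4 sets out a general mixed-model ANOVA approach. The reason given for it is "correlated observations due to study subjects potentially contributing measurements of more than one single tooth site to the analysis". Repeated visits to the same site are not part of that reason. The only random effect named is the subject: "Subjects will be included as a random effect on the analyses that include multiple observations per subject".

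Three specific aims add repeated visits and take an interaction with time as the main test:

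- SA-3: soft tissue healing at weeks 1, 2, 4 and 8, tested by group by time.
- SA-8: a soft tissue index at final restoration, 12 and 24 months, tested by implant type by time.
- SA-9: crestal bone, tested by surface by time. Its covariance is described only as follows: "The analysis for the SA will be mixed-model ANOVA, accounting for multiple observations per subject".

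On the design, section 3.1 states: "Each participant may have up to four non-adjacent sites selected for inclusion as study treatment sites". Section 4.4 assigns the implant collar by participant: "Subjects with multiple sites will receive the same implant design in all study sites". Section 12.5 sizes SA-8 and SA-9 by a t-test in which "sd refers to the within-group standard deviation of changes across time", and uses a sample size reduced for correlation between sites. Section 12.3 says that bone height at 12 and 24 months is compared with insertion to obtain changes from baseline, measured on the mesial and distal surfaces.

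**The concern.** The data have three levels (subject, site, visit), and the plan names a variance term for one of them. For a test of change over time, two consequences follow if the subject term is an intercept.

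1. Lasting differences between the sites of one person cancel from each site's own change. A model without a site term leaves them in the residual. The error term is then too large and the test too conservative.
2. A subject intercept also cancels from change. If two sites in one mouth change together, the model treats those changes as independent. The error term is then too small and the test too liberal.

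The power section assumes the reverse on both counts. Using the standard deviation of changes removes lasting site differences, and the reduced sample size allows for correlated changes. The test described in 12.4 is therefore not the one that was sized.

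At stake are the group comparison of soft tissue healing (SA-3) and the implant comparisons of SA-8 and SA-9. SA-9 is the main test of crestal bone under Hypothesis III, alongside SA-7 and SA-8.

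**Working it through.** **Inputs from the documents.** 80 participants, 20 per extraction group (3.1). One to four sites each (3.1), with planning averages of 1.5 or 2 (12.5). ICC between sites up to 0.50 (12.5). Two-sided 5% tests (12.5). Effective sample size 50 per implant group (12.5). Four visits for SA-3; three for SA-8; three for SA-9 if the levels at insertion, 12 and 24 months are modelled.

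**Assumptions.** Equal allocation to the two collars, and the split of variance into S (subject), ST (subject-by-visit), K (site within subject) and e (residual).

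**The plan's own figure.** Power for a 0.50 sd difference in change: 0.50 × √(50/2) − 1.96 = 0.54, giving 70.5% (69.7% with the t distribution) against the stated 70%. At 0.565 sd: 2.825 − 1.96 = 0.865, giving 80.6% (79.9%) against 80%. Both reproduce, for an analysis of changes with clustering allowed for.

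**Error term in a balanced case.** Take n = 80 subjects, m = 2 sites, T = 3 visits and two arms. The correct error mean square for arm by time is e + m·ST. A subject-intercept model pools three strata:

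| Stratum | df | Expected mean square |
|---|---|---|
| Site within subject | 80 × 1 = 80 | e + 3K |
| Subject by visit | 2 × 78 = 156 | e + 2ST |
| Site by visit | 80 × 1 × 2 = 160 | e |

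- Lasting site differences only (K = 0.25, ST = 0, e = 0.25): pooled = (80 × 1.00 + 156 × 0.25 + 160 × 0.25)/396 = 0.402; correct = 0.25. SE ratio √(0.402/0.25) = 1.27; type I error about 1%.
- Correlated changes only (K = 0, ST = 0.25, e = 0.25): pooled = (80 × 0.25 + 156 × 0.75 + 160 × 0.25)/396 = 0.447; correct = 0.75. SE ratio 0.77; type I error about 17%.
- Both (K = 0.25, ST = 0.125, e = 0.25): pooled = (80 × 1.00 + 156 × 0.50 + 160 × 0.25)/396 = 0.50, equal to the correct 0.50. In this layout the two distortions cancel exactly when K = 2·ST.

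**Simulation with unequal site numbers.** One to four sites, 3,000 runs per case, total variance 1, ICC 0.50. Type I error of the subject-only test at nominal 5%:

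| Assumed split | SA-8/9, mean 1.5 sites | SA-8/9, mean 2 | SA-3, mean 1.5 | SA-3, mean 2 |
|---|---|---|---|---|
| K = 0, ST = 0 | 5.1% | 4.5% | 5.0% | 4.9% |
| S 0.5, K 0.25, e 0.25 | 1.5% | 1.0% | 0.6% | 0.1% |
| S 0.25, ST 0.25, K 0 to 0.4, rest e | 8.0–10.4% | 9.9–16.4% | 8.3–16.0% | 16.9–29.3% |

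With one site each, every split gave 4.2% to 5.3%. Averaging sites within participant before testing gave 4.0% to 5.8% throughout.

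**More extreme and mixed splits, implant comparison.**

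- Site variance equal to subject variance and error sd 0.5, two visits: type I error 0.1% or less. Power for a 0.5 sd-of-change difference was 25–27%, against 77–88% with site in the model. The ICC here is 1/(1 + 1 + 0.25) = 0.44, and site variance is four times error variance, so this is a strong case.
- Changes correlated and no lasting site differences: separate simulations gave 11% to 21%.
- S/K/ST/e of 0.375/0.25/0.125/0.25: 5.8–7.7%. With 0.4/0.3/0.1/0.2: 3.5–4.6%.

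**Whether a site term alone is enough.** With correlated changes, adding only a site effect still gave 10–15%. The subject-by-visit term is needed as well.

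**The case against.** Section 12.4 describes a general approach. It excludes no further term and does not say that the subject effect is an intercept only. That is fair, and the point is therefore limited to what the plan names. It does not remove the problem. An analyst who follows the text literally fits the subject-only model, and one who adds terms after seeing the data chooses among models with different p-values.

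For SA-9, section 12.3 allows the response to be each site's change from insertion. Lasting site differences then cancel before modelling, and a subject effect does represent changes shared by sites in one mouth. This stands, and on this reading the problem is smaller. In the strong site-variance case above, type I error was 1.1–1.9%, still conservative because a site's two changes share one baseline reading. The plan does not say which response is used.

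A reader might infer that the tests are wrong whenever anyone has more than one site. The calculations contradict this: the error is correct with neither extra variance source, and the two can offset. A reader might also infer that the direction is known, or that this one test settles Hypothesis III. The documents give no variance components, so the direction is open. SA-7 and SA-8 also sit under that hypothesis, and the primary implant parameter in 12.3 is survival, which this issue does not touch.

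**Conclusion.** The concern holds as a gap with possible consequences for validity. The random effect named in 12.4 does not describe the data for SA-3, SA-8 and, on the raw-level reading, SA-9, and it does not match the analysis that 12.5 sized. For the implant comparisons, with an average of 1.5 to 2 sites, type I error ranges from about 0% to about 20%; for SA-3 the range was 0.1% to 29.3%. All of these rest on assumed variance splits, and some plausible mixes stay near 5%. With one site per participant and no serial correlation between visits, the tests are about correct; serial correlation was not simulated. Lasting site differences are plausible because eligible sites include both premolars and maxillary anterior teeth, but their size is not given. Severity: should-fix.

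**What to change.** In section 12.4, for SA-3, SA-8 and SA-9:

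- Name random effects for subject, site within subject and subject-by-visit. Alternatively, use an unstructured visit covariance with subject-clustered robust standard errors.
- Use subject-level denominator degrees of freedom for the interaction tests.
- State whether the SA-9 response is bone level or change from insertion. With changes at 12 and 24 months as the response, a surface-by-time term compares only the movement between those two visits.
- Average the mesial and distal readings for each implant.
- If the model does not converge, average sites within participant at each visit and run a repeated-measures analysis of the participant means. This fallback works for three or four visits.

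The cost is SAP wording and a few lines of model code. No new data are needed.
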